Screening/Baseline Evaluation

The visit encompasses completion of the screening-baseline packet to determine eligibility following consent procedures. Once the informed consent process has been completed, all remaining procedures can occur. It is not permitted to collect biological samples (blood) from a patient before informed consent has been obtained.

To decide the order in which measures and procedures will be completed, consider which items are completed by coordinators and which are completed by physicians. An efficient approach to the screening visit could involve a study physician completing the NPI and other interview measures with the patient's informant in one exam room, while the study coordinator completes the MMSE, vitals, blood draws, and EKG with the patient in a separate exam room. Note that the study physician will need to complete a physical exam with the patient as part of the screening visit. Alternatively, the coordinator may do all procedures sequentially, scheduling in a brief period for the study physician to complete the clinical examination. Visit structures may vary participant to participant. Some participants cannot be left alone, and so coordinators may consider allowing them to stay present during the caretaker interviews, if this is not disruptive to the reporting. Similarly, caretakers may vary in the amount of information they provide during interviews, and this can be taken into account for time estimates. It is good to remain flexible during each visit.

At the conclusion of the screening/baseline visit, study staff should know which inclusion/exclusion criteria are met and which are not, with the exception of those that require lab results to determine. If at this point the patient has not been excluded, the participant should be informed that after all lab results are returned, the research pharmacy will ship the study drug kit directly to the participant's home.

The following assessments will be completed at the screening/baseline visit:

Physician-completed:

- Clinical Evaluation & Physical Examination
- CGI (Global Impression of Severity)
- SCID and CSSR-S
- Lawson IDLs
- Simpson-Angus Scale
- Treatment Emergent Symptoms Scale (baseline measure for comparison)

Coordinator-completed

- Confirmation of diagnoses*
- Medical History & Concomitant Medications*
- MMSE (Folstein Mini Mental Exam)
- MDRS (Mattis Dementia rating Scale)
- FBI (Frontal Behavioral Inventory)**
- Zarit Caregiver Burden Interview**

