Outcome measures and covariates. Primary outcome: agitation/aggression score (domain score on the Neuropsychiatric Inventory (NPI), continuous measure from 0-12, longitudinal); Secondary outcome: response (dichotomous, based on 30% decrease in NPI core score (sum of domains for motor activity and agitation/aggression) plus a CGI-C score of much improved or very much improved, longitudinal); Exploratory outcome motor activity score on the NPI. Covariates/Predictor variables: 1) demographic characteristics (e.g., gender, race, age); 2) baseline measures of the corresponding outcomes. Other Measures:1) tolerability, as measured by emergent side effects (TESS scores and adverse events) over the course of the 12 week trial; 2) brain derived neurotrophic factor (BDNF) serum levels.

Sample size and randomization: The randomization will be carried out by the statistician and implemented by the pharmacist, who are both otherwise independent of the research team. The randomization sequences will be balanced in blocks of random size to prevent clinicians from guessing what the next patient's treatment might be.

Modeling longitudinal data and testing hypotheses. Modeling longitudinal data and testing hypotheses. All tests will be two-sided; α =0.05; intent-to-treat with data included for all patients with ≥1 post-baseline assessment. We will use generalized linear mixed models (GLMMs; SAS PROC GLIMMIX) for longitudinal data to evaluate study aims. Models will include fixed effects for treatment group, time, group x time interaction, and any baseline covariates found to be unbalanced despite randomization. Prior to analysis, we will examine all variables at all time points for outliers and inconsistencies and examine their distributions.⁴¹⁻⁴³

Primary hypothesis: *Lithium will significantly reduce agitation/aggression as compared to placebo.*

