Tolerability: We will assess the tolerability of low dose lithium by assessing emergent side effects over the course of the 12-week trial on lithium compared to placebo. We will compute descriptive statistics of tolerability measures in each treatment group and provide both point estimates and their confidence intervals. We will test whether the change in TESS score from baseline to week 12 differs significantly in the lithium and placebo arms by a t-test.

Biomarker Hypothesis. Increases in BDNF serum levels will be associated with decreases in agitation/aggression and repetitive behaviors. The relationship between change in BDNF serum levels (defined as baseline minus endpoint of active treatment) and the changes in agitation/aggression score and motor activity score (defined as baseline minus treatment endpoint) will be tested using correlation analyses.

Power Analysis. Given the proof-of-concept nature of this study as a pilot, effect sizes with 95% confidence intervals rather than statistical significance testing will be the primary results of interest. The overarching aim is to demonstrate feasibility for conducting a larger trial which would then be used to adequately test efficacy.³³ Nevertheless, we provide some guidance regarding the statistical power available for testing differences between treatments. With n=60 patients randomized (30 to lithium, 30 to placebo) we conservatively examine power below assuming attrition will be 20% (i.e. 48 completers) though our past studies have all had attrition <20% and all available longitudinal data will be used for all individuals regardless of whether they complete the 12 weeks. For the primary outcome of agitation/aggression score measured by the NPI, we will have 80% power to detect a medium to large treatment effect size of 0.58-0.83 with the range depending on the within person correlation over time. Additionally, for responder status, we will have >80% power to detect a difference between, for example, a 15% response rate and a 50% response rate at 12 weeks. Differences among other exploratory outcomes and tolerability measures will be detectable with similar power.

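### TESS tolerability is compared by a change-score t-test; adjusting week-12 TESS for the baseline already collected is generally more precise and costs one degree of freedom

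*Combined protocol and SAP*

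**What the plan says.** All references are to the combined protocol and SAP.

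- **Tolerability** (Statistical Procedures and Data Analysis): the question put to the data is "whether the change in TESS score from baseline to week 12 differs significantly in the lithium and placebo arms by a t-test". No covariate is attached to this test. The same paragraph promises descriptive statistics by arm, with point estimates and confidence intervals.
- **Screening/Baseline Evaluation**: the physician-completed list includes the "Treatment Emergent Symptoms Scale (baseline measure for comparison"). Randomisation follows only after eligibility is confirmed, so this is a true baseline. The Week 12 Visit list includes TESS again.
- **Outcome measures and covariates**: the baseline value of each outcome is named among the covariates or predictors. The general mixed-model text adds only baseline covariates found to be imbalanced. Neither statement is carried into the TESS test. Tolerability is placed under other measures, after the primary, secondary and exploratory outcomes.
- **Modeling longitudinal data and testing hypotheses**: "All tests will be two-sided; α =0.05; intent-to-treat with data included for all patients with ≥1 post-baseline assessment".
- **Power Analysis**: for NPI agitation/aggression, "we will have 80% power to detect a medium to large treatment effect size of 0.58-0.83". The spread is attributed to how strongly a patient's repeated scores correlate, for which no number is given. Tolerability is said to have similar power. Effect sizes with 95% intervals are ranked above significance tests.

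**The concern.** A change score gives baseline a weight of exactly 1. That weight is best only when the regression slope of week-12 TESS on baseline TESS is 1. Otherwise the subtraction leaves avoidable noise in the arm comparison. With equal SDs and a correlation below 0.5, subtracting baseline is even noisier than ignoring it.

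The Introduction names side effects alongside efficacy as what the trial examines, and only 60 patients are to be randomised. The plan also puts interval estimates first. A noisier between-arm TESS estimate means a wider interval, and a real excess of symptoms on lithium becomes easier to miss. The data needed to avoid this are already collected.

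**Working it through.** **Inputs from the documents.** 30 patients per arm; 20% attrition, so 48 completers (24 per arm); two-sided α = 0.05; 80% power.

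**Inputs not in the documents, so assumed.** r, the correlation of baseline with week-12 TESS: 0.3, 0.5, 0.7. k, the baseline SD divided by the week-12 SD: 0.75, 1, 1.25.

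**Step 1: the plan's own figure.** With 24 per arm, a two-sample t-test (noncentral t) has 80.4% power at a standardised effect of 0.83, and its detectable effect at 80% power is 0.826. The upper end of the stated range reproduces. The lower end needs a within-person correlation that is not given. Averaging six post-baseline visits with a common correlation of 0.4 gives 0.826 × √((1 + 5 × 0.4)/6) = 0.584, so 0.58 is reachable but cannot be confirmed. Both figures concern the NPI score, not TESS.

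**Step 2: variances, in units of the week-12 variance.**

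- Change score: 1 + k² − 2rk
- Baseline-adjusted: 1 − r²
- Difference: (k − r)², which is never negative and is zero when r = k (slope r/k = 1)
- Proportional cut from adjusting: 1 − (1 − r²)/(1 + k² − 2rk); with k = 1 this is (1 − r)/2

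| k | r = 0.3 | r = 0.5 | r = 0.7 |
|---|---|---|---|
| 0.75 | 1 − 0.91/1.1125 = 18% | 1 − 0.75/0.8125 = 8% | 1 − 0.51/0.5125 = 0.5% |
| 1 | 1 − 0.91/1.40 = 35% | 1 − 0.75/1.00 = 25% | 1 − 0.51/0.60 = 15% |
| 1.25 | 1 − 0.91/1.8125 = 50% | 1 − 0.75/1.3125 = 43% | 1 − 0.51/0.8125 = 37% |

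**Step 3: what the k = 1 row means.** The variance ratio, adjusted to change score, is (1 + r)/2 = 0.65, 0.75, 0.85. The interval narrows by 1 − √ratio = 19%, 13%, 8%. The t-test would need 2/(1 + r) − 1 = 54%, 33%, 18% more patients for the same precision.

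**Step 4: small-sample cost.** An approximate inflation of the adjusted variance by 1 + 1/(48 − 4) = 1.023 changes the k = 1 cuts to 33.5%, 23.3% and 13.1%. In the least favourable cell (k = 0.75, r = 0.7), 0.995 × 1.023 = 1.018, so adjustment would there be about 2% worse.

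**Step 5: detectable effects, 24 per arm, 80% power, k = 1, in week-12 SD units.**

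| Analysis | r = 0.3 | r = 0.5 | r = 0.7 |
|---|---|---|---|
| Change score, 0.826 × √(2(1 − r)) | 0.98 | 0.83 | 0.64 |
| Adjusted, 0.826 × √(1 − r²) | 0.79 | 0.72 | 0.59 |

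**The case against.** The case for leaving the plan alone has weight. Under randomisation the change-score t-test is unbiased and valid. The trial is a pilot, and tolerability is not a primary, secondary or exploratory outcome. Adverse events are monitored and reported as well, so detection of harm does not rest on this test. The per-arm intervals in the Tolerability paragraph do not depend on the between-arm method; only the interval for the arm difference does. All of this stands, and it lowers the importance of the point. It does not remove the gain.

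Four stronger readings are tempting, and the documents do not support them.

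- A reader might infer that a change score is efficient only at a correlation of 1, and so is always clearly worse. That is true only with equal SDs. A scale of treatment-emergent symptoms may well vary less before treatment than after it. At k = 0.75 and r = 0.75 the large-sample gain is nil.
- A reader might take 15–35% as a firm figure. It depends on assumed correlations and equal SDs. Over the values tried, the range is about 0.5% to 50%.
- A reader might infer that the plan forgoes 15–35% of the variance reduction that baseline adjustment offers. That is a different quantity. Against ignoring baseline, with equal SDs, adjustment saves r² and the change score saves 2r − 1. The share forgone is (1 − r)²/r², which is 544%, 100% and 18% at r = 0.3, 0.5 and 0.7.
- A reader might infer that the similar-power statement for tolerability is wrong, because 0.98 lies outside 0.58–0.83. The plan does not say which SD standardises its effect sizes, and it gives no TESS correlation, so that cannot be shown.

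The covariate list does mention baseline values of the corresponding outcomes, but nothing there clearly alters a test separately specified as a t-test on change.

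**Conclusion.** The point holds as a matter of precision, not validity. The planned TESS comparison imposes a baseline coefficient of 1 where one could be estimated, and in large samples estimating it is never less precise. The figures in Step 2 are variance cuts relative to the change-score estimate. They apply to a single week-12 measurement and do not carry over unchanged to a multi-visit TESS average. Because both r and k are assumed, the defensible statement is a range from negligible to about one half. Importance is low, but so is the cost of the change.

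**What to change.** In the Tolerability paragraph, replace the t-test with a linear model of week-12 TESS on treatment arm and baseline TESS. Report the adjusted lithium-minus-placebo difference with its 95% confidence interval. Name week 12 explicitly as the outcome, so that the analysis stays as well defined as the current text. The by-arm descriptive statistics can remain as they are.

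The cost is one sentence of SAP wording and one degree of freedom. No additional data, visits or patients are needed. The change should be made before unblinded TESS data are analysed.

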While study staff is to remain blinded to drug assignment (lithium/placebo) during the 12 week trial, patients will have lithium blood levels taken at weeks (2, 4,) 6, 8, and 12 for safety monitoring and dosage adjustment. We will follow the procedures successfully used for blinded lithium levels in controlled trials in mood disorders. A physician independent of the study will receive lithium levels. This unblinded physician will provide the actual lithium level to the study physician for patients randomized to lithium, and make up a comparable sham level for patients on placebo. This sham level will vary from low to high levels and will be largely based on the number of pills taken by the patient. Target serum lithium level is 0.4 - 0.6 mmol/L. Based on the blood level received and clinical response and tolerability, the study physician will adjust the number of pills at study visits.

[name] will act as the unblinded RA. At each study visit where lithium levels are drawn (weeks 2,4,6,8,12) the study coordinator will give the serum lithium/sham lithium level form to the unblinded RA with the following information already filled in: current daily dose of lithium/placebo, how administered, number of hours between last oral dose and blood draw, date blood drawn. The unblinded RA will receive lab results for patients active in the protocol, including their real lithium level results, via the CALM website. The unblinded RA will email both the partially completed serum lithium/sham lithium level form, and that patient's lab results to the unblinded physician ([name]). The unblinded physician will complete the form by writing either a real lithium level or a sham lithium level and then signing and dating the form. At this time, the unblinded physician will also enter the real lithium/sham lithium level into the updated randomization spreadsheet provided to them by the NYSPI pharmacy. The unblinded physician will email the completed form to the unblended RA, who will forward it to the study coordinator

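### The only tolerability test uses TESS change at week 12, leaves out the scores from weeks 2 to 10 and does not say how early-termination scores count, so it may miss earlier side effects

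*Combined protocol and SAP*

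**What the plan says.** Under Statistical Procedures and Data Analysis, the outcomes paragraph lists, among the other measures, "tolerability, as measured by emergent side effects (TESS scores and adverse events) over the course of the 12 week trial". The Tolerability paragraph repeats that scope: "assessing emergent side effects over the course of the 12-week trial on lithium compared to placebo". It then makes two commitments. The first is descriptive: "We will compute descriptive statistics of tolerability measures in each treatment group and provide both point estimates and their confidence intervals". The second is the only hypothesis test on tolerability, of whether the "change in TESS score from baseline to week 12 differs significantly in the lithium and placebo arms by a t-test". The general rule is "All tests will be two-sided; α =0.05", with everyone who has at least one post-baseline assessment in the analysis.

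TESS is a baseline item at the Screening/Baseline Visit and is listed in each of the Week 2, 4, 6, 8, 10 and 12 Visit sections. Dose responds to side effects throughout. The Introduction makes response and side effects the main guide to dose, and the section on lithium/sham levels says that, given level, response and tolerability, "the study physician will adjust the number of pills at study visits".

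For patients who leave, the Introduction schedules an assessment at protocol exit. Alternate Scenarios (items 2 to 4) calls for all week-12 measures at early termination. It files them as week 12/early termination and also records the nearest study interval.

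**The concern.** The stated quantity is side-effect burden over a period; the tested quantity is its value at the end of that period. They agree only if the lithium–placebo difference is about the same throughout. The plan gives a reason why it might not be: a symptom that prompts a change in the number of pills can ease before week 12, and its score then never reaches the test.

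The second gap is who is in the test. Read strictly, a patient who leaves at week 3 has no week-12 score and drops out of the comparison, despite the rule on at least one post-baseline assessment. Read by the database label, that patient's week-3 score stands in for week 12. These are different comparisons, and the choice should not be left until after the data are seen.

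At stake is the side-effect estimate that a larger trial would use. The Introduction names side effects beside efficacy as what the study examines.

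**Working it through.** **1. Collected against tested.** There are six scheduled post-baseline TESS scores (weeks 2, 4, 6, 8, 10, 12); the test uses one. The Introduction's list of assessments omits week 10, but the Week 10 Visit section includes TESS. On the shorter list the test would omit four of five.

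**2. The plan's own power figure.** The Power Analysis gives 80% power for 0.58 to 0.83 SD on the primary outcome and says tolerability measures have similar power. With 20% attrition, 30 × 0.8 = 24 per arm.
- SE of a difference in SD units = √(2/24) = 0.289.
- At 0.83: 0.83/0.289 = 2.88; t-test power (46 df, two-sided 0.05) = 80.4%. The upper end is reproduced.
- At 0.58: 0.58/0.289 = 2.01; power = 50%. The lower end needs repeated measures. The normal-approximation detectable effect is 0.809, and (0.58/0.809)² = 0.514. Setting (1 + 5ρ)/6 = 0.514 for six visits gives ρ ≈ 0.42.

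So a single-time-point t-test reaches only the upper end of the plan's range.

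**3. Effect of the time profile.** The documents give no SD, effect or correlation for TESS. Assumed: SD of each score 1, peak effect 0.83, equal correlation ρ of 0.4 to 0.6 between any two scores (baseline included), 24 per arm with complete data. Variance per patient:
- Planned change to week 12: 2(1 − ρ) = 1.2 to 0.8; SE = √(2 × variance/24) = 0.316 to 0.258.
- Six-visit average, baseline-adjusted: (1 + 5ρ)/6 − ρ² = 0.340 to 0.307; SE 0.168 to 0.160.
- Week 12 alone, baseline-adjusted: 1 − ρ² = 0.84 to 0.64; SE 0.265 to 0.231.

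Profiles as multiples of 0.83 at weeks 2 to 12: rise and hold (0.25, 0.5, 0.75, 1, 1, 1; mean 0.75); fade (0.5, 0.75, 1, 1, 0.75, 0.5; mean 0.75); linear rise (1/6 to 1; mean 0.583).

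| Profile | Week-12 effect | Average effect | Planned t-test | Visit average | Week-12 contrast, adjusted |
|---|---|---|---|---|---|
| Rise to week 8, hold | 0.83 | 0.62 | 73–88% | 95–97% | 87–94% |
| Fade to half | 0.415 | 0.62 | 25–35% | 95–97% | 34–42% |
| Linear rise | 0.83 | 0.48 | 73–88% | 80–84% | 87–94% |

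Part of the gain comes from baseline adjustment. An unadjusted average change has variance (1 + 5ρ)/6 + 1 − 2ρ = 0.700 to 0.467, SE 0.242 to 0.197. Its power is 71–87% in the first two profiles and 50–67% in the third.

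**4. Effect of who is counted.** A simulation with 30 per arm, SD of change 1, reference effect 0.83 and 20% random placebo dropout (all assumed) gave these week-12 differences and t-test powers:
- Random dropout in both arms: 0.83, 81%.
- Dose adjustment removes 25% or 50% of the effect: 0.63, 57%; 0.42, 29%.
- Worst 20% of lithium patients leave, completers only: 0.49, 47%. Check: cutting the top fifth of a normal distribution lowers its mean by 0.280/0.8 = 0.35, and 0.83 − 0.35 = 0.48.
- The same leavers, exit scores kept (all 30 per arm analysed): 0.83, 89%.
- Worst 20% leave in both arms: 0.83, 91%.
- Week-12 effect 25% above reference after upward titration, random dropout: 1.04, 94%.

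**The case against.** A reader might infer that the test is biased towards no difference, because doses have been cut and intolerant patients have gone by week 12. The documents do not support that, for three reasons.

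First, leavers are assessed at exit with all week-12 measures, which include TESS, and the record carries a week-12 label. If those scores are used, symptom-driven dropout need not shrink the difference, as step 4 shows. Some exit scores may be taken after the drug was stopped, since item 2 of Alternate Scenarios puts the measures at the next visit. How often is unknown.

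Second, titration runs upward, with the maximum daily dose reachable from week 6 and an increase still possible at week 8. Exposure, and with it side effects, could be highest late. Increases do depend on tolerance, but no passage shows that side effects peak early and fade.

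Third, the plan does not rest on this p-value. It promises TESS and adverse-event descriptives with confidence intervals, and the Power Analysis puts effect sizes with intervals ahead of significance tests.

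All three stand against a claim of demonstrated bias. They do not close the gap. The descriptive commitment names no time point, summary or between-arm contrast, and an effect size taken at week 12 alone has the same limited scope as its test. The plan's general statement on mixed models does not settle it either: the models written out are for the NPI scores and response, with the groups contrasted at week 12.

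**Conclusion.** The point holds as a mismatch between aim and test. The only tolerability test covers one of six scheduled post-baseline TESS scores, and the status of the week 12/early termination record is undefined. With dose adjusted for side effects before week 12, the test may miss or understate side effects that occurred earlier.

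Direction and size are not established. Under the assumptions in step 3, the planned test's power runs from 25–35% (fading effect) to 73–88% (effect at its peak at week 12). In step 4, the expected difference runs from 0.42 to 1.04 SD around a reference of 0.83, according to dose adjustment, titration and the handling of leavers. These figures show how far the result depends on matters the plan leaves open; they do not predict this trial. This is a secondary analysis in a pilot, so the change is worth making but is not critical.

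**What to change.** Make the tested quantity the lithium–placebo difference in TESS averaged over all post-baseline visits. Estimate it from a mixed model with treatment, categorical visit, treatment × visit and baseline TESS, in every randomised patient with at least one post-baseline TESS. Place each early-termination score at its nearest study interval, which the database already records, and state a rule for two scores falling in one interval. Report the estimate with a 95% confidence interval and give the week-12 contrast from the same model.

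Report worst post-baseline TESS descriptively only, because a maximum grows with the number of visits attended. At ρ = 0.5 and no true effect, the expected maximum of six scores exceeds that of two by √0.5 × (1.267 − 0.564) = 0.50 SD. If 20% of lithium patients left after two visits, the lithium mean would fall by 0.2 × 0.50 = 0.10 SD.

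The cost is SAP wording; the data are already collected and clinical management is untouched. There is a small downside: if side effects build steadily to week 12, the average dilutes the late effect (0.48 against 0.83 SD in step 3). The week-12 contrast still shows it.

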The following linear mixed effects model will be used: $Y_{ij} = \beta 0 + \beta 1 I T R T + \beta 2t + \beta 3t^* I T R T + \beta 4X_i + \beta 4X_i$ bi + $\epsilon i j$ where Yij is the agitation/aggression score for the *i*th subject at *t*week, *t* =0, 2,...,12, *yi0* is agitation/aggression at baseline, *liTRT* is the indicator variable for randomized condition (placebo vs. lithium), an indicator of recruitment site (Columbia University Medical Center and Johns Hopkins School of Medicine), and any baseline covariates exhibiting imbalance after randomization, bi is a random intercept to account for repeated measures across time within the patient, and $\epsilon i j$ is a random error term. Significant interaction $t^* liTRT$ indicates that the changes in agitation/aggression in each treatment group is different over time (which corresponds to rejecting the null hypothesis that β 3= 0). The effect of time will be estimated for each group separately and the groups will be compared (using contrast) at the last time point t=12. Secondary hypothesis: Lithium will have greater proportion of responders compared to placebo. We will test whether the probability of response by end of active treatment differs significantly in the lithium and placebo groups by a chi-square test. In addition, we will test whether change in the probability of response differs across treatment groups by longitudinal analysis. We will use the generalized linear mixed effects model: logit(Yij) = $\beta 0 + \beta 1$ liTRT+ $\beta 2t$ + $\beta 3t^{*}$ /*iTRT*+ $\beta 4Xi$ + *bi* + ϵij where Yij is the a binary variable indicating response for the *i*th subject at t week, t = 2, 4, ..., 12. We will first test significance of the treatment effect by testing the group by time interaction.

Exploratory Hypothesis. Lithium will significantly reduce repetitive behaviors as compared to placebo. We will use the same model in the analyses for the primary hypothesis where Yij is the motor activity score for the *i*th subject at *t* week, *t* =0, 2,...,12.

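### The BDNF correlation gives treatment arm no stated role; if lithium shifts both BDNF and symptoms, a pooled correlation cannot show that BDNF tracks symptoms beyond assignment to lithium

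*Combined protocol and SAP*

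**What the plan says.** Under Statistical Procedures and Data Analysis, the Biomarker Hypothesis paragraph states: "Increases in BDNF serum levels will be associated with decreases in agitation/aggression and repetitive behaviors". Both changes are taken as baseline minus end of treatment, so a rise in BDNF is negative, a fall in symptoms is positive, and the hypothesised correlation is negative. The relationship "will be tested using correlation analyses". That is the whole specification: it names no arm term, stratification, partial correlation or per-arm estimate.

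Treatment does appear elsewhere in the section. The paragraph on modelling longitudinal data says "Models will include fixed effects for treatment group, time, group x time interaction", but this describes the mixed models for repeated measures. No sentence extends it to the BDNF correlation. BDNF is scheduled only at baseline and week 12 (Assays by visit), so each patient has one change value and the longitudinal model does not carry over.

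The plan also hypothesises a lithium effect on both symptom scores used in the correlations: "Lithium will significantly reduce agitation/aggression as compared to placebo" and "Lithium will significantly reduce repetitive behaviors as compared to placebo". It states no hypothesis and no effect size for lithium on BDNF.

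**The concern.** Arm may be a common cause of both changes. If lithium raises BDNF and, by whatever route, lowers agitation, the pooled scatter is two clouds displaced along a diagonal. The pooled correlation is then non-zero even when BDNF and symptoms are unrelated among lithium patients and unrelated among placebo patients. Under the plan's sign convention the induced correlation is negative, which is the direction hypothesised.

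What is at stake is how the result is used. The Power Analysis paragraph presents the trial as a pilot for a larger study. A pooled BDNF correlation that only restates the arm difference would tell the designers of that study nothing about BDNF that the treatment comparisons had not already told them.

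**Working it through.** **Inputs from the documents.** "With n=60 patients randomized (30 to lithium, 30 to placebo"; 20% attrition, leaving 48 completers, taken here as 24 per arm; "All tests will be two-sided; α =0.05"; detectable effect on the agitation/aggression score 0.58 to 0.83 at 80% power (all from Statistical Procedures and Data Analysis).

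**Inputs assumed.** The lithium effect on BDNF change, d1, in within-arm SD units: 0 to 1.5, since the documents give none. The plan's 0.58 and 0.83 serve as the lithium effect on score change, d2, in within-arm SD units. They are detectable effects, not forecasts. True within-arm correlation: zero.

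**The plan's own figure.** For two means with 24 per arm, d = (1.960 + 0.842) × √(2/24) = 2.802 × 0.2887 = 0.81 by the normal approximation, and 0.83 by the noncentral t. The upper end reproduces. The lower end depends on a within-person correlation ρ that the plan does not state. Averaging six post-baseline visits gives 0.81 × √((1 + 5ρ)/6), which equals 0.58 at ρ of about 0.42, so that end is attainable but cannot be checked uniquely.

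**Induced correlation.** With equal arms and no within-arm association, the pooled covariance is −d1·d2/4 and the pooled variances are 1 + d1²/4 and 1 + d2²/4. Hence

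r = −(d1·d2/4) / √[(1 + d1²/4)(1 + d2²/4)].

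- d1 = 0.5, d2 = 0.58: 0.0725 / √(1.0625 × 1.0841) = 0.0725 / 1.0733 = 0.068 in size.
- d1 = 1.5, d2 = 0.83: 0.31125 / √(1.5625 × 1.1722) = 0.31125 / 1.3534 = 0.230 in size.

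**How often it is significant.** 40,000 simulated trials per case, normal data, 24 per arm, Pearson test at two-sided 0.05:

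| BDNF shift d1 (assumed) | r at d2 = 0.58 | significant | r at d2 = 0.83 | significant |
|---|---|---|---|---|
| 0 | 0.000 | 5.1% | 0.000 | 5.1% |
| 0.3 | −0.041 | 6.0% | −0.057 | 6.7% |
| 0.5 | −0.068 | 7.2% | −0.093 | 9.5% |
| 0.83 | −0.107 | 11.4% | −0.147 | 16.9% |
| 1.0 | −0.125 | 13.5% | −0.171 | 21.8% |
| 1.5 | −0.167 | 20.8% | −0.230 | 35.7% |

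In the same simulations the partial correlation given arm averaged about zero and was significant in 4.8 to 5.2% of trials in every case.

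**Sensitivity to the number analysed.** Early termination visits take all week 12 samples (Alternate Scenarios), so more than 48 patients may contribute a pair. With all 60 and d2 = 0.83, the rates at d1 = 0.83, 1.0 and 1.5 are 20.4%, 26.5% and 43.8%. The induced r does not depend on the sample size.

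**The case against.** The strongest reply is that the hypothesis as worded speaks only of an association. If lithium moves both measures, BDNF change and symptom change really are associated across the trial's patients, and a pooled correlation detects that correctly. A reader might infer that the 7 to 36% are false positives for the stated hypothesis. The documents do not support that: the plan never states a within-arm null, and what may be absent is a within-arm association, which is a different quantity. Nor do the documents say that the correlation will be read as evidence of mechanism. BDNF is listed among other measures, and neither mediation nor surrogacy is mentioned. This reply stands, and it limits the point to what the pooled estimate can show.

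Four further replies have some force.

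- The plan does not say that the arms are pooled, and a per-arm analysis is not excluded. True, but pooling is the plain reading, and if something else was intended it needs saying.
- The induced correlation is modest. With 48 patients, a 95% interval around a correlation near zero is about ±0.28, wider than every induced value in the table. That stands.
- The pilot puts effect sizes and confidence intervals ahead of significance tests. This does not remove the issue, because the interval would be centred on the same displaced coefficient.
- Adjusting for arm discards the between-arm component, which belongs to the association if lithium acts partly through BDNF. This is a fair reason to keep the pooled figure beside the adjusted one.

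**Conclusion.** The point holds as a minor, nearly free improvement. The plan leaves the role of arm in the BDNF correlation unstated. On the plain reading, the estimate mixes the between-arm difference with any within-arm relationship and cannot separate them. For 48 patients and an assumed BDNF shift of 0.5 to 1.5 SD, the induced correlation is about 0.07 to 0.17 in size with 7 to 21% significant at a score effect of 0.58 SD, and about 0.09 to 0.23 with 10 to 36% significant at 0.83 SD. After adjustment for arm the rate is about 5%.

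A reader might go further and infer that the biomarker result is most likely to mislead whenever lithium works. That does not follow. Lithium must also move BDNF, on which the documents are silent; if it reduces agitation and leaves BDNF unchanged, the rate stays at about 5%. The upper figures need a BDNF shift of 1.5 SD, larger than any clinical effect size the plan gives. The primary, secondary and exploratory efficacy analyses do not depend on this correlation.

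**What to change.** In the Biomarker Hypothesis paragraph, make the main estimate for each symptom score either a partial correlation given treatment arm, or a regression of score change on BDNF change with arm as covariate, reported with its 95% confidence interval. Show the estimate within each arm as well. Keep the pooled correlation as a descriptive figure, labelled as including the between-arm difference.

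The cost is a sentence in the SAP and one degree of freedom (45 instead of 46 with 48 patients). Arm is known for every randomised patient, so no new data, visit or sample is needed. The adjusted estimate would show whether BDNF tracks symptoms beyond assignment; it would not by itself establish mediation, and the report should not present it as doing so.
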